3. PATIENT SELECTION

3.1 Eligibility Criteria

3.1.1 Patients must have histologically confirmed malignancy with brain metastases and are recommended palliative WBRT.

3.1.2 Life expectancy of greater than 2 months to allow completion of study treatment and assessment of dose-limiting toxicity.

3.1.3 Age \geq 18 years. Because no dosing or adverse event data are currently available on the use of IPdR in patients $<$ 18 years of age, children are excluded from this study, but will be eligible for future pediatric trials.

3.1.4 ECOG performance status \leq 2 (Karnofsky \geq 60%, see Appendix A).

3.1.5 Patients must have normal organ and marrow function as defined below:

- leukocytes \geq 3,000/mcL
- absolute neutrophil count \geq 1,000/mcL
- platelets \geq 100,000/mcL
- calculated creatinine clearance \geq 45 mL/min/1.73 m²

- Total bilirubin, AST (SGOT) and ALT (SGPT):
If no known liver metastases:
Total bilirubin $<$ 1.5 x institutional upper limit of normal (ULN), AST/SGOT and ALT/SGPT both $<$ 2 x ULN.

If known liver metastases, then:
Total bilirubin $<$ 2.5 x ULN, AST/SGOT and ALT/SGPT both $<$ 5 x ULN.

3.1.6 HIV+ patients with CD4 counts \geq 250 cells/mm³ on anti-viral therapy are eligible for the study.

3.1.7 Negative urine or serum pregnancy test result for females of child bearing potential only.
Note: The effects of IPdR on the developing human fetus are unknown. For this reason and because radiation therapy is known to be teratogenic, women of child-bearing potential and men must agree to use adequate contraception (hormonal or barrier method of birth control; abstinence) prior to study entry and for the duration of study participation. Should a woman become pregnant or suspect she is pregnant while she or her partner is participating in this study, she should inform her treating physician immediately. Men and women treated or enrolled on this protocol must also agree to use adequate contraception prior to the study, for the duration of study participation, and 4 months after completion of IPdR administration.

3.1.8 Ability to understand and the willingness to sign a written informed consent document.

3.2 Exclusion Criteria

- 3.2.1 Presence of diffuse lepto or pachy meningeal carcinomatosis (focal/localized involvement from limited meningeal based metastases are acceptable), greater than 1 cm mid-line shift, uncal herniation, or severe hemorrhage/hydrocephalus (small intra-lesional or anticipated surgical cavity hemorrhage is acceptable). Patients with seizure at presentation who have been started on Levetiracetam and have been stable for 48 hours prior to study registration are eligible at the discretion of treating physician.
- 3.2.2 Patients who have received systemic cytotoxic chemotherapy or approved oral targeted therapy or immunotherapy for 2 weeks, or other investigational agents for 3 weeks (4 half-lives for any oral targeted agents), or radiotherapy to a non-brain site for 2 weeks before initiation of IPdR therapy. Patients who have recovered from serious (CTCAE grade 3 or more higher) to grade 1 or less adverse events from the previous therapies are eligible. Prior/current/future hormonal therapy and/or bisphosphonates are permitted with no minimum interval to initiation of study therapy. If indicated, patients can receive palliative radiation therapy to a non-brain site concurrent or immediately post-study treatment with no minimum interval to initiation of study therapy.
- 3.2.3 Patients must not have received prior whole brain radiation therapy. Previous SRS/SRT done at least 3 weeks from the planned start of IPdR therapy is acceptable. SRS/SRT/fractionated boosts or neurosurgery can be performed once the DLT assessment has been completed, if felt clinically necessary.
- 3.2.4 Patients with primary tumors including germ cell tumor, or lymphoma/leukemia.
- 3.2.5 Patients who are receiving any other investigational agent.
- 3.2.6 Patients needing more than 8 mg dexamethasone per day at the time of start of WBRT will not be eligible to participate in the study. However, patients will be allowed entry into the study if it is medically safe to reduce the daily dose of dexamethasone to 8 mg or less from the day of the start of WBRT. The dexamethasone dose for such patients may be increased beyond 8 mg per day during the course of treatment if medically necessary. This increased need for dose should be communicated to the study's Principal Investigator, [name] at the University of Maryland.
- 3.2.7 History of allergic reactions attributed to compounds of similar chemical or biologic composition to IPdR.
- 3.2.8 Uncontrolled intercurrent illness if it would increase the risk of toxicity or limit compliance with study requirements. This includes, but is not limited to, ongoing uncontrolled serious infection requiring i.v. antibiotics, progressive congestive heart failure, unstable angina pectoris, or psychiatric illness/social situations that would limit compliance with study requirements.

3.2.9 Pregnant women are excluded from this study because IPdR is an agent with the potential for teratogenic or abortifacient effects. Because there is an unknown but potential risk for adverse events in nursing infants secondary to treatment of the mother with IPdR, breastfeeding should be discontinued if the mother is treated with IPdR.

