5. TREATMENT PLAN

5.1 Agent Administration

Treatment will be administered on an outpatient basis. Reported adverse events and potential risks are described in Section 7. Appropriate dose modifications are described in Section 6. No investigational or commercial agents or therapies other than those described below may be administered with the intent to treat the patient's malignancy. 5-iodo-2-pyrimidinone-2'-deoxyribose (IPdR) (NSC 726188) will be delivered by oral (po) administration in capsule form once daily x 28 days. The capsules will be taken on an empty stomach (either 1 hour before or 2 hours after meals).

IPdR will be administered alone without WBRT during Week 1 (7 calendar days) and with WBRT during Weeks 2-4. On days when IPdR and WBRT are given concurrently, IPdR should be administered within 30 minutes to 2 hours prior to WBRT.

Because IPdR is an orally administered agent patients will be requested to maintain a medication diary of each dose of medication. The medication diary will be returned to clinic staff at the end of each course.

Since the IPdR half-life is <1 day, 5 half-lives will be less than 1 week. Hence, an observation period up to D35 (D1 being 1st day of IPdR) is required to assess toxicity before enrolling a patient at the next IPdR dose level. Patients will be allowed to initiate systemic therapy per clinician preference after the D35 assessment.

The starting dose for IPdR for Phase 1 testing is based on the most sensitive (lower MTD) of the two animal species tested, *i.e.* ferrets and rats [44, 45]. The MTD for IPdR in ferrets, the most sensitive species, was determined to be ≤ 150 mg/kg/d for 14 days[45], which is equivalent to 850 mg/M²/day for 14 days. The human equivalent dose (HED) is also 850 mg/M²/day, the same as the ferret dose, based on body surface area (BSA).[48] Based on these calculations and pre-clinical animal data, 1/10th of the MTD is 85 mg/M²/day (150 mg), the starting dose for this trial.

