5.1.4.2 Technical Factors

Treatment will be delivered with megavoltage (MV) machines of energy ranging from 4 MV to 6 MV photons. Patients will be planned and treated using three-dimensional conformal radiation technique (3D-CRT). Field-in-field approaches to

3DCRT to optimize homogeneity are permitted. Intensity Modulated Radiotherapy (IMRT) with or without hippocampal avoidance (Fixed-gantry IMRT, helical tomotherapy or VMAT) will be allowed per institutional protocols. Partial brain cone down, stereotactic radiosurgery boost, electron therapy, particle therapy, or brachytherapy boost are not permissible during the course of the study treatment and until the DLT assessments are complete. However, patients will be eligible to undergo SRS/SRT/fractionated boosts or neurosurgery, once the DLT assessment has been completed, if felt clinically necessary.

5.1.4.3 Localization, Simulation, Immobilization and Dose prescription.

The patient will be treated in the supine position to allow planning and delivery of WBRT. A head-holding device that is transparent to x-rays must ensure adequate immobilization during therapy and ensure daily treatment reproducibility. A non-contrast treatment-planning CT scan of the entire head region extending into neck should be obtained. When using hippocampal avoidance WBRT, it is recommended the axial slice thickness should match the MRI axial slice thickness as much as possible (preferred 1.5 mm). The treatment-planning CT scan must be acquired with the patient in the same position and immobilization device as for treatment.

For 3D-CRT, the target volume will include the entire cranial contents, with flashing beyond skin and adequate margin on the skull base as visualized on the simulator or portal films to account for beam penumbra and day-to-day set-up variation. Attempts will be made to exclude the lenses and the anterior globe from the beam either by field arrangement or shielding. ‘Helmet’ portals with customized immobilization and shielding are permitted. The dose is specified as the target dose, which shall be the dose on the central x-ray at mid-separation for two opposed coaxial equally weighted beams. “Compensating beams” that block hot spots (these hot spots are typically present along midline due to less tissue present in these regions compared to mid-brain) are allowed to achieve better dose homogeneity. All portals shall be treated during each treatment session.

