10. STUDY CALENDAR

Pre-treatment laboratory tests and exams must be completed, eligibility confirmed and the patient registered within 6 weeks; baseline brain imaging evaluations to be done within 4-6 weeks before start of the study treatment. Study treatment should begin within 2 weeks after registration. Vital signs and performance status should be obtained within 1 week before the start of study treatment.

	Pre-Study treatment	Wk 1	Wk 2	Wk 3	Wk 4	DLT Assessment On D35 (or \leq 3 days after D35)	Follow-Up ⁱ	Off Study ^k
Informed consent	X							
WBRT planning	X ^a	X ^a						
IPdR ^R		X	X	X	X			
WBRT			X	X	X			
Urine or serum pregnancy test (if indicated)	X							
History and physical exam ^b	X	X	X	X	X	X	X	X
Adverse Events ^b		X	X	X	X	X	X	X
Blood work ^c	X	X	X	X	X	X		
PK studies ^R		X ^d		X ^e	X ^e			
Up to 6 RP2D/MTD patients only (expansion cohort): Blood for granulocytes^R		X ^f	X ^f					
Up to 6 RP2D/MTD patients only (expansion cohort): Extracranial tumor biopsy mandatory^{l,R}			X ^f					
MRI brain w/ IV contrast ^h	X						X ^g	X
Neurocognitive and Quality of life evaluation ^R	X					X ^j	X ^j	X

a. May be performed prior to study registration per standard of care

b. Baseline physical examinations are to be conducted within 1 week prior to start of protocol therapy. In the event that the patient's condition is

deteriorating, these evaluations should be repeated within 48 hours prior to the initiation of therapy. Physical examination includes vital signs (pulse, blood pressure, temperature), concomitant medications, performance status, weight and at pre-study only, height. The evaluations are recommended to be done towards the end of the respective week.

- c. Blood work to include CBC with differential count, comprehensive metabolic profile including serum albumin, alkaline phosphatase, total bilirubin, BUN, creatinine, total protein, SGOT [AST], SGPT [ALT]. The evaluations are recommended to be done towards the end of the respective week.
- d. On Day 1, a pre-study blood will be obtained and then sampling will be done at 30, 60, 120 and 240 minutes and 24 hours (just prior to Day 2 dosing) following the initial po drug administration. A five minute positive or negative margin on each of the above times on Day 1 (30 through 240 minutes) and 10 min for the 24 hours timepoint is acceptable.

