11.1.2 Disease Parameters

Measurable disease. Measurable lesions are defined as those that can be accurately measured in at least one dimension (longest diameter to be recorded) as ≥ 10 mm (≥ 1 cm) with MRI. All tumor measurements must be recorded in millimeters (or decimal fractions of centimeters).

Non-measurable disease. All other lesions including small lesions (longest diameter <10 mm [< 1 cm]) are considered non-measurable disease.

Target lesions. All measurable lesions up to a maximum of 5 lesions in total should be identified as **target lesions** and recorded and measured at baseline. Target lesions should be selected on the basis of their size (lesions with the longest diameter) and should be those that lend themselves to reproducible repeated measurements. It may be the case that, on occasion, the largest lesion does not lend itself to reproducible measurement in which circumstance the next largest lesion which can be measured reproducibly should be selected. A sum of the longest diameters for all target lesions will be calculated and reported as the baseline sum diameters. The baseline sum diameters will be used as reference to further characterize any objective tumor regression in the measurable dimension of the disease.

Non-target lesions. All other lesions including any measurable lesions over and above the 5 target lesions should be identified as **non-target lesions** and should also be recorded at baseline. Measurements of these lesions are not required, but the presence, absence, or in rare cases unequivocal progression of each should be noted throughout follow-up.

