11.1.4.3 Evaluation of Best Overall Response

The best overall response is the best response recorded from the start of the treatment until disease progression/recurrence (taking as reference for progressive disease the smallest measurements recorded since the treatment started). The patient's best response assignment will depend on the achievement of measurement criteria.

For Patients with Measurable Disease (i.e., Target Disease)

Target Lesions	Non-Target Lesions	New Lesions	Overall Response
CR	CR	No	CR
CR	Non-CR/ Non-PD	No	PR
CR	Not evaluated	No	PR
PR	Non-CR/ Non-PD/ Not evaluated	No	PR
SD	Non-CR/ Non-PD/ Not evaluated	No	SD
PD	Any	Yes or No	PD
Any	PD*	Yes or No	PD
Any	Any	Yes	PD

For Patients with Non-Measurable Disease (i.e., Non-Target Disease)

Non-Target Lesions	New Lesions	Overall Response
CR	No	CR
Non-CR/non-PD	No	Non-CR/non-PD*
Not all evaluated	No	not evaluated
Unequivocal PD	Yes or No	PD
Any	Yes	PD

* ‘Non-CR/non-PD’ is preferred over ‘stable disease’ for non-target disease since SD is increasingly used as an endpoint for assessment of efficacy in some trials so to assign this category when no lesions can be measured is not advised

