13.4.4 Intracranial progression free survival (icPFS) and Overall Survival (OS)

These will be explored using the Kaplan-Meier method. For estimation of icPFS, patients alive without intracranial progression at last follow-up will be censored at the date of the last radiologic assessment whereas intracranial progression or death will be scored as events. The icPFS estimates at 6 months with their standard error of the estimate will be reported. For calculation of OS, patients alive at last follow-up will be censored.

13.4.5 Incidence of delayed neurological toxicity at 2, 4 and 6-months (\pm 1 week) post-completion of WBRT (for patients without intracranial progression) including:

- a. Delayed-recall through HVLT-R**
- b. Quality of life as measured by the FACT-BR**

REFERENCES

1. Posner, J.B. and N.L. Chernik, Intracranial metastases from systemic cancer. *Adv Neurol*, 1978. 19: p. 579-92.
2. Stewart, B.W., P. Kleihues, and I.A.f.R.o. Cancer, *World cancer report*. Vol. 57. 2003: IARC press Lyon.
3. Gaspar, L.E., et al., Validation of the RTOG recursive partitioning analysis (RPA) classification for brain metastases. *Int J Radiat Oncol Biol Phys*, 2000. 47(4): p. 1001-6.
4. Nussbaum, E.S., et al., Brain metastases. Histology, multiplicity, surgery, and survival. *Cancer*, 1996. 78(8): p. 1781-8.
5. Sperduto, P.W., et al., Summary report on the graded prognostic assessment: an accurate and facile diagnosis-specific tool to estimate survival for patients with brain metastases. *J Clin Oncol*, 2012. 30(4): p. 419-25.
6. Tsao, M.N., et al., Whole brain radiotherapy for the treatment of newly diagnosed multiple brain metastases. *Cochrane Database Syst Rev*, 2012. 4: p. CD003869.
7. Young, D.F., et al., Rapid-course radiation therapy of cerebral metastases: results and complications. *Cancer*, 1974. 34(4): p. 1069-76.
8. Rades, D., et al., Dose escalation beyond 30 grays in 10 fractions for patients with multiple brain metastases. *Cancer*, 2007. 110(6): p. 1345-50.
9. Chao, J.H., R. Phillips, and J.J. Nickson, Roentgen-ray therapy of cerebral metastases. *Cancer*, 1954. 7(4): p. 682-9.
10. Gaspar, L.E., et al., The role of whole brain radiation therapy in the management of newly diagnosed brain metastases: a systematic review and evidence-based clinical practice guideline. *J Neurooncol*, 2010. 96(1): p. 17-32.

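### Local brain treatment allowed after D35 without progression has no rule in best response or intracranial PFS, so its effect can be credited to IPdR plus WBRT

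*Combined protocol and SAP*

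**What the plan says.** **What is permitted**
- Section 5.1.4.2 bars boosts and radiosurgery during study treatment and until the toxicity assessment, then adds: "However, patients will be eligible to undergo SRS/SRT/fractionated boosts or neurosurgery, once the DLT assessment has been completed, if felt clinically necessary". Section 3.2.3 gives the same permission: "SRS/SRT/fractionated boosts or neurosurgery can be performed once the DLT assessment has been completed, if felt clinically necessary". The calendar in section 10 fixes the time: "DLT Assessment On D35", or up to 3 days later.
- Section 5.1 also opens the door to drugs: "Patients will be allowed to initiate systemic therapy per clinician preference after the D35 assessment".
- Before the study, section 3.2.3 states: "Previous SRS/SRT done at least 3 weeks from the planned start of IPdR therapy is acceptable".

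**How efficacy is scored**
- Target lesions (11.1.2): "All measurable lesions up to a maximum of 5 lesions in total should be identified as" targets. Section 11 ties them to the high-dose volume, which under WBRT takes in essentially any measurable brain lesion. Nothing is said about local treatment before or after baseline.
- Best response (11.1.4.3): "The best overall response is the best response recorded from the start of the treatment until disease progression/recurrence". Section 13.4.1 uses the same window and restricts the analysis to Part 2 patients.
- Intracranial PFS (11.1.6) runs from treatment start to progression or death. For censoring, 13.4.4 says: "patients alive without intracranial progression at last follow-up will be censored at the date of the last radiologic assessment".
- Imaging (5.5 and calendar note g): the 6-month MRI after WBRT is required; the two-monthly scans before it are only recommended.

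**The concern.** Objectives 1.2.1 and 1.2.2 ask about anti-tumour activity and 6-month intracranial control with IPdR and WBRT. After D35 a site may resect, boost or radiosurgically treat the lesions on which both are measured, on clinical judgement alone. If that happens before progression is recorded, the scoring rules do not react. Shrinkage or removal of a target counts towards response, and the patient remains event-free for intracranial PFS.

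The protocol shows awareness of later treatments elsewhere. Sections 5.1.3 and 5.2 say that later procedures and therapies must be considered when judging late neurotoxicity. No matching sentence exists for efficacy.

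At stake are the response summary, overall and by tumour group, and the 6-month intracranial PFS estimate. Section 13.4.1 says the number of responses may point to tumour types worth studying further. Within a tumour group, one or two patients change the picture.

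**Working it through.** **1. The plan's own figures.** There is no target, power or expected value for response or intracranial PFS to reproduce. The only operating characteristics (5.1.3) concern DLTs. They do reproduce: at a DLT rate of 0.3, escalation is 0.7³ + 3 × 0.3 × 0.7⁵ = 0.494, and the chance of at most 5 DLTs in 16 is 0.660. They do not bear on this point.

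**2. Following one patient through the rules**

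| Event after D35 | Before recorded progression | After recorded progression |
|---|---|---|
| Target boosted, diameter sum falls 30% | PR under 11.1.4.1 | Best response has already ended |
| Sole target resected | Target-lesion CR; overall CR only if non-target lesions are also gone, otherwise PR | Best response has already ended |
| Intracranial PFS | No event; follow-up continues | Event already counted |

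Local brain treatment is not among the removal criteria in 5.4 and 5.6. Section 11.1.1 makes every patient evaluable for response from the first IPdR dose. So nothing takes the left-hand cases out.

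**3. Timing.** The last WBRT fraction is on D26 (schema). Taking 6 months as 183 days:
- Required MRI: 26 + 183 = D209, window D195 to D223. This is 209 − 35 = 174 days after D35.
- Six-month landmark from treatment start: D183. Local treatment is open for 183 − 35 = 148 of 183 days (81%).

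A procedure can therefore come before the only mandatory response scan.

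**4. Response rate.** Section 13.2 plans 19 to 25 patients, of whom 2 are in Part 1. Assuming expansion patients count with Part 2, the denominator is 17 to 23. One misattributed response moves the rate by 1/17 = 5.9 points or 1/23 = 4.3 points.

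Illustration, with the 5 true responders and the 2 misattributed responses both assumed: 5/17 = 29.4% (exact 95% CI 10.3 to 56.0) becomes 7/17 = 41.2% (18.4 to 67.1).

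**5. Intracranial PFS.** Let q be the share given local treatment while event-free, S the 6-month intracranial PFS without it, and r the share of their would-be events that it removes. If treated patients otherwise have average risk, the shift is q(1 − S)r. None of the three is in the documents. Assumed ranges are q = 0.1 to 0.3, S = 0.4 to 0.6, r = 0.5 to 1:
- smallest: 0.1 × 0.4 × 0.5 = 2 points
- largest: 0.3 × 0.6 × 1 = 18 points

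**6. Radiosurgery before enrolment.** Section 11.1.3 allows a baseline scan up to 4 weeks before treatment, and 3.2.3 allows radiosurgery 3 weeks before. A scan on Day −28 followed by radiosurgery on Day −21 is inside both outer limits, and the lesion may still be chosen as a target. A treated lesion may still be shrinking or may swell, so the direction of the error is not known.

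**The case against.** **Importance.** These are secondary endpoints in a single-arm phase 1 trial. Section 13.4.1 calls for simple descriptive summaries, and section 2.5 leaves efficacy to later studies. This stands, and it limits the weight of the point. A reader might infer that response counts select the Phase 2 tumour types, but 13.4.1 only says they may indicate further evaluation.

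**Recoverability.** Section 11.1.7 has the radiology investigator review responses together with patient files and images, and calendar note h sends Part 2 scans for central review. A reader might infer that the effect can never be separated afterwards; that goes too far. What is missing is an instruction to the reviewer, and a guarantee that a scan exists before the procedure.

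**Interim scans.** Section 11.1.6 expects intracranial PFS to be assessed at 2, 4, 6 and 8 months. Where recommended scans are done and show progression before local treatment, there is no bias. This stands, but those scans are optional.

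**Size.** One could assume that 10 to 30% of 17 patients (about 2 to 5) are treated locally and read off 2/17 to 5/17, or 12 to 29 points. That needs every one of them to be a non-responder turned into a responder. The documents support neither the rate nor the conversion.

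**Resection example.** Section 2.5.1 describes non-surgical patients with multiple metastases, so removal of a sole target giving an overall CR is likely to be rare. Boosts and radiosurgery are not affected by this argument.

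**RECIST and pre-study radiosurgery.** Section 11.1 adopts the RECIST 1.1 guideline, whose content on previously treated lesions cannot be checked from these documents. Section 11.1.3 also wants baseline imaging as near to treatment as possible, which the Day −28 example strains. A claim of upward bias from pre-study radiosurgery is therefore not supported.

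**Planned intracranial PFS.** It is a coherent estimate of outcome under whatever treatment follows. This stands, and the planned analysis should be kept.

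**Conclusion.** The gap is real for local brain treatment given after D35 and before recorded progression. As written, the plan can credit that treatment's effect to IPdR plus WBRT, in both best response and intracranial PFS. For this part the bias is upward.

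The only size the documents support is per patient: 5.9 points of response rate at 17 patients, 4.3 at 23, if expansion patients are counted with Part 2. The 2 to 18 point range for intracranial PFS rests wholly on assumed inputs. Pre-study radiosurgery is a lesser, related gap of uncertain direction. Systemic therapy started after D35 raises the same attribution question.

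The RP2D decision rests on DLTs and is untouched. The change is worth making because a few sentences prevent a wrong response classification, but it is not critical to the primary objective.

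**What to change.** All changes concern analysis and data capture; permitted care is unchanged.

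- **Data capture:** record the date, type and lesion of every brain-directed procedure, before and after study treatment.
- **11.1.4.3 and 13.4.1:** count best response only from MRIs before the first post-D35 local brain procedure given without progression. Keep patients with no earlier post-baseline MRI in the denominator as not evaluable, counted as non-responders. Report how many patients are affected.
- **13.4.1:** flag responses first seen after new systemic therapy.
- **13.4.4:** keep the planned intracranial PFS as the main estimate. Add a sensitivity estimate censored at the last MRI before such a procedure, noting that this censoring may be informative because clinical need selects the patients.
- **11.1.2:** do not choose as a target a lesion given SRS/SRT before enrolment unless it has since progressed, and measure baseline on an MRI taken after that treatment.

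The cost is a few sentences in sections 11 and 13.4 and a short procedure record. The downside is that a few responses stop counting, so the estimates become less favourable. Because interim MRIs are optional, some affected patients will have no usable scan and will count as non-responders.
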